### 1.2 Rationale for the Study

Randomized controlled trials (RCTs) are the "gold standard" for generating evidence of the efficacy and safety of a drug. However, enrolment criteria, timelines, and atypical comparators of RCTs limit relevance to standard clinical practice. Real world data (RWD) provide longitudinal information on comparative effectiveness and tolerability of drugs, as well as data on their impact on resource use, medical costs, pharmaco-economic outcomes, and patient-reported outcomes. While the randomized nature of the RCT ensures its high internal validity by removing bias, their 'controlled' nature casts a doubt on their generalizability to the real-world population. It is for this reason that trials done in a real-life setting post the marketing authorization of a drug are increasingly required [16].

Akynzeo® received authorization from Health Canada in September 2017 for its use in:

- the prevention of acute and delayed nausea and vomiting associated with highly emetogenic cancer chemotherapy and
- the prevention of acute nausea and vomiting associated with moderately emetogenic cancer chemotherapy that is uncontrolled by a 5-HT3 receptor antagonist alone

This study is designed to collect clinical data on the real-world use of Akynzeo® in Canada. The aim of the study is to support clinical data from the development program by the generation of real world evidence on the effectiveness, safety and additional parameters of Akynzeo® in a local clinical setting. As a non-interventional study [17], the inclusion of patients will be carried out only after the physician has freely decided – on the basis of the patient’s individual situation – that the patient will receive Akynzeo® as antiemetic therapy for the prevention of CINV. The investigation on the effectiveness and safety profile of Akynzeo® is to take place under everyday clinical practice conditions. The parameters of interest for this study will be collected by means of a patient diary and then documented in a dedicated electronic case report form by the appropriate personnel. Moreover, patient exclusion criteria will reflect the Product Monograph (PM), including “Cautions” and “Warnings” and no additional clinical investigations will be performed compared to the routine clinical practice in order to reflect real world use and increase study data generalizability.

This prospective, non-interventional study (NIS) enables the collection of anonymized data feeding a larger global registry reflecting patients’ exposure to Akynzeo®. A registry is a database of patients exposed to the same specific drug to determine if that drug has a special impact [17,18], to determine real life effectiveness and quality of care [19].

### 1.3 Study Drug - Combination of Palonosetron and Netupitant

NEPA (Akynzeo®) was developed as an oral fixed combination of the highly selective NK1RA, netupitant (300 mg), and the clinically [8] and pharmacologically [9] distinct 5-HT3RA, palonosetron (0.5mg).

Pivotal clinical studies described in section 1.4, which represented the basis for the marketing authorization of NEPA, have demonstrated superiority of oral NEPA plus dexamethasone over oral palonosetron plus dexamethasone in preventing CINV during the acute (0-24h), delayed (25-120h), and overall (0-120h) phases following both cisplatin- [10] and anthracycline-cyclophosphamide (AC)-based chemotherapy [11,12]. In addition, NEPA was shown to be efficacious over multiple cycles in patients receiving either HEC or moderately emetogenic chemotherapy (MEC) [13].

Akynzeo®, which is the trade name of the medicinal product mentioned above, was approved on 27 May 2015 by the European Medicines Agency for prevention of acute and delayed nausea and vomiting in highly emetogenic cisplatin-based cancer chemotherapy and moderately emetogenic cancer chemotherapy in adults [14] and on 27 September 2017 by Health Canada in combination with dexamethasone, as once-per-cycle treatment in adult patients for the prevention of acute and delayed nausea and vomiting associated with highly emetogenic cancer chemotherapy [15].

## 1.4 Clinical Studies

Three pivotal clinical studies were published simultaneously in the Journal "Annals of Oncology" in July 2014. The studies demonstrated that a single oral dose of the combination netupitant and palonosetron (NEPA) is efficacious and safe for use in the prevention of CINV.

Study	Design	Patient population & chemotherapy	Treatment arms	Number of CTX cycles	Objective of the study
Study 1: Hesketh et al. [10]	Double-blind, randomized, Phase II dose-finding study	N=694; chemotherapy-naive patients; cisplatin-based HEC	NEPA 100mg + Dex NEPA 200mg + Dex NEPA 300 mg + Dex PALO oral + Dex (APR + OND iv + Dex; explorative)	One cycle	NEPA dose-finding; efficacy of NEPA
Study 2: Aapro et al. [11]	Double-blind, randomized, Phase III study	N=1455; chemotherapy-naive patients; AC-based CTX	NEPA + Dex PALO oral + Dex	Multiple cycles	Superiority of NEPA compared to PALO
Study 3: Gralla et al. [13]	Double-blind, randomized Phase III study	N=413; chemotherapy-naive patients; all HEC or MEC (except AC)	NEPA 300 mg + Dex PALO oral + Dex APR + PALO oral + Dex (3:1 randomization)	Multiple cycles	Safety of NEPA over multiple cycles, non-inferiority compared to SoC

### Study 1: NEPA – dose-finding Phase II (Hesketh et al. 2014)

The dose of netupitant (300 mg) administered in combination with 0.5 mg palonosetron was selected based on the results of a Phase II dose-finding study. This multinational, randomized double-blind study assessed three different single oral doses of netupitant (100 mg, 200 mg and 300 mg) in combination with a fixed oral dose of palonosetron (0.5 mg) and oral dexamethasone compared to oral palonosetron (0.5 mg) and oral dexamethasone, prior to a single cycle administration of cisplatin-based, highly emetogenic chemotherapy (HEC). Solely for exploratory purposes, a treatment arm with the triple combination of aprepitant, ondansetron and dexamethasone were included. The study population consisted of 679 adult male or female chemotherapy-naive patients with a histologically or cytologically confirmed solid tumour. The objective of the study was to determine the optimal dose for netupitant in combination with 0.5 mg palonosetron for effective and safe prevention of CINV, whereby the complete response (CR) rate was measured after 0-120 hours. The highest proportion of patients with CR was in the group treated with 300 mg netupitant plus palonosetron (89.6 %), followed by the group with 200 mg (87.6 %) and the group with 100 mg (87.4 %). The lowest proportion of patients with CR was in the group treated with palonosetron alone (76.5 %). All doses of netupitant in combination with palonosetron were superior to palonosetron monotherapy. The dose of 300 mg netupitant showed an advantage over the lower doses. Compared to the regimen with aprepitant and ondansetron, there was also a higher proportion of responsive patients in the 300 mg netupitant group.

Treatment-related adverse events (AEs) occurred in a total of 333 of the 679 patients (49 %). The total proportion of patients with AEs was comparable in the five treatment groups and not dependent on the netupitant dose (100 mg: 40.7 %; 200 mg: 51.4 %; 300 mg: 50 %; palonosetron monotherapy: 50 %; aprepitant: 53 %). The analysis of AEs, laboratory parameters, vital signs and 12-lead ECG showed no safety concerns for the administration of palonosetron in combination with netupitant at doses of 100 mg, 200 mg or 300 mg. Based on the results obtained for efficacy and safety in this Phase II dose-finding study, 300 mg oral netupitant in combination with 0.5 mg of oral palonosetron has been identified as the optimum dosage for the combination. [10]

### **Study 2: Superiority of NEPA in comparison with palonosetron (Aapro et al. 2014)**

Based on the results of the dose-finding study by Hesketh et al., the fixed dose combination NEPA, consisting of 300 mg netupitant and 0.5 mg palonosetron, was investigated in a subsequent double-blind, multicentre, randomized Phase III Study with regard to efficacy in comparison with palonosetron. 1455 chemotherapy-naive patients with a median age of 54 years, who received an anthracycline-cyclophosphamide chemotherapy (AC-based) over several cycles, were included. On day 1 of each chemotherapy (CT) cycle, the patients were treated either with NEPA (300 mg netupitant / 0.5 mg palonosetron) + 12 mg dexamethasone or 0.5 mg oral palonosetron + 20 mg dexamethasone. The primary endpoint was complete response defined as "no vomiting, no rescue medication" in the delayed phase (> 24 – 120 h after CT). Of the 724 evaluable patients in the NEPA-arm, 88.4 % showed a complete response in the acute phase and 76.9 % in the delayed phase. In the Palo-arm with 725 evaluable patients, the response rates were 85 % for the acute phase and 69.5 % for the delayed phase of CINV. NEPA showed a statistically significant higher response rate over the overall period with 74.3 % compared to 66.6 % for PALO (p = 0.001).

NEPA was also statistically significantly superior to PALO for the secondary endpoints "no vomiting" (a), "no severe nausea" (b) and "complete control" (c), both in the delayed phase and over the entire period for a): 81.8 % and 79.8 % vs. 75.6 % and 72.1 %, for b): 76.9 % and 74.6 % vs. 71.3 % and 69.1 % and for c): 67.3 % and 63.8 % vs. 60.3 % and 57.9 %.

There was no impairment of regular daily activities (based on the Functional Living Index - emesis - questionnaire). Overall, the frequency, nature and intensity of the adverse events were comparable between the two study arms. In 8.1 % of patients treated with NEPA there were treatment-associated side effects (PALO arm: 7.2 %), but there were no serious adverse events, no discontinuations of therapy and no deaths. The most common adverse events were headache and constipation.

The results of the study showed that in all phases after treatment with moderately emetogenic chemotherapy (AC-based considered as MEC at the time of the study), a single oral dose of NEPA in combination with a single dose of dexamethasone leads to better complete response rates than a single oral dose of palonosetron in combination with a single dose of dexamethasone. The authors concluded that future guideline-compliant antiemetic treatment could be simplified on the basis of the fixed dose combination. [11]

### **Study 3: Safety and efficacy of NEPA over repeated cycles (Gralla et al. 2014)**

Another pivotal study for clinical use of NEPA was also published by Gralla and colleagues in 2014. The multicentre, randomized, double-blind phase III study included 413 adult patients with solid tumours of different entities, which had not been previously treated with chemotherapy. Of these patients, 76 % received a non-AC-based MEC (carboplatin, oxaliplatin, doxorubicin,

cyclophosphamide, irinotecan, epirubicin, daunorubicin) and 24 % a HEC (> 90 % cisplatin, the rest dacarbazine, carmustine). Of the 412 evaluable patients in a 3:1 randomization, 308 patients were treated on Day 1 of the CTX with NEPA (300 mg netupitant + 0.5 mg palonosetron) + 12 mg dexamethasone. The remaining 104 patients were treated with 125 mg aprepitant + 0.5 mg palonosetron + 12 mg dexamethasone on day 1 of the CT followed by 80 mg aprepitant + 8 mg dexamethasone (only in case of HEC) on days 2 and 3. The primary endpoint was defined as the safety profile of NEPA administered over at least 6 CT cycles. The efficacy (complete response and prevention of severe nausea) was determined as a secondary endpoint.

Antiemetic treatment was administered in a total of 1961 CT cycles, including 1446 with NEPA and 515 with APR / PALO. 98 % of patients completed cycle 1, 75 % completed 4 cycles and 40 % of patients completed 6 cycles.

The most common treatment-related adverse events were constipation (3.6 % NEPA vs. 1 % APR / PALO) and headache (in each case 1 % for NEPA and APR / PALO), whereby the frequency did not increase with increasing number of cycles. Overall, the rate of side effects during treatment in cycle 1 was 5.2 % (n = 308) for NEPA vs. 2.9 % for APR / PALO (n = 104). These rates fell by cycle 6 to 1.6 % for NEPA (n = 124) and 0 % for APR / PALO (n = 43) on account of the decreasing number of cases. There were no concerns with regard to the cardiac safety of NEPA.

Overall, complete response rates (no vomiting, no rescue medication) were high in both study arms over all chemotherapy cycles. NEPA showed a slight, persistent numerical advantage of 2-7 % compared to APR / PALO.

In this study, Gralla et al. were able to demonstrate consistent efficacy of NEPA associated with good tolerability over multiple cycles of highly and moderately emetogenic chemotherapies [13].

## 1.5 Study Population

This study will enroll adult male or female chemotherapy patients of various cancer types who are scheduled to receive chemotherapy with high emetogenic potential for a maximum of 2 days.

## 2 STUDY OBJECTIVES

The primary study objective is to generate Real World Evidence (RWE) on the quality of life by means of the FLIE questionnaire on administration of Akynzeo® in highly emetogenic chemotherapy (HEC), and to generate Real World Evidence in support of existing clinical trial data.

The study will also assess effectiveness and safety of NEPA in the real world setting for the prevention of Chemotherapy Induced Nausea and Vomiting (CINV) in patients receiving highly emetogenic chemotherapy).

## 2.1 Primary Outcome: Functional Living Index - Emesis (FLIE)

The quality of life of patients can be collected by means of the FLIE questionnaire on administration of Akynzeo® during chemotherapy with moderately and highly emetogenic agents.

The Functional Living Index – Emesis questionnaire is a patient reported outcome (PRO) validated tool with the objective of assessing the impact of chemotherapy-induced nausea and vomiting on patient's daily function.

It consists of a nausea domain and a vomiting domain of nine items each where the patient should rate how much nausea and vomiting have affected the quality of life. For each question the patient will rate how much nausea (or vomiting) has affected an aspect of his quality of life during the past five days. Each question uses a visual analogue scale (VAS).

The investigator shall be responsible for explaining to the patient how the questionnaire should be correctly completed.

## 2.2 Secondary Outcomes

The response to Akynzeo® and the necessity for use of a rescue medication will be recorded to evaluate effectiveness. The medicinal products used as rescue medication will also be recorded. The following parameters will be calculated from information recorded in the patient diary:

- Complete Response (CR): no emetic episode and no use of rescue medication in the overall period (0-120h/Day 1-5)
- Severity of nausea (daily from Day 1 to Day 5) using a VAS scale (Visual Analogue Scale)
- Time to failure (time to first emetic episode or time to rescue)
- Use of rescue medication (daily from Day 1 to Day 5)

The collection of safety data and adverse events AEs in connection with administration of Akynzeo® will be performed.

## 2.3 Exploratory Outcomes

Health economic and outcomes research data will be collected and recoded on the diary card specifically emergency department (ED) visits and hospitalizations.

Work Productivity Activity Impairment scale for Nausea and Vomiting (WPAI-NV) will be collected on day 5 of each cycle.

## 3 STUDY DESIGN

### 3.1 Study Overview

This two year (approximately), multi-centre, prospective, observational real-world study is designed to collect data on the use of Akynzeo® (netupitant/palonosetron) for the prevention of nausea and vomiting in oncology patients receiving highly emetogenic chemotherapy (HEC).

The visit schedule is comprised of 6 study visits (Table 1):

- Visit 1/Screening (4 weeks to 0 weeks prior to Visit 2)
- Visit 2: (Day of/but prior to 1st chemotherapy treatment administration)

- Visit 3: (Day of/but prior to 2nd chemotherapy treatment administration)
- Visit 4: (Day of/but prior to 3rd, chemotherapy treatment administration)
- Visit 5: (Day of/but prior to 4th, chemotherapy treatment administration)
- Visit 6/Final Visit

Visit 1 and 2 can be combined as determined by the investigator. Patients will report the daily occurrence and intensity of nausea and vomiting, rescue medications, adverse events (excluding nausea and vomiting) in a diary from Day 1 (chemotherapy treatment day) to Day 5/time point 0-120 hours post chemotherapy administration of each observation period.

Safety events occurring between chemotherapy cycles will be reported by the patient. Patient will have a follow up period of 28 days post the last-chemotherapy cycle.

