EXCLUSION CRITERIA (as per Contraindications in the approved Canadian Product Monograph)	
 
• Women of child bearing potential who are pregnant, planning on becoming pregnant or breast feeding.
 
• Hypersensitivity to active substances, excipients or other ingredients of Akynzeo®.
 
• Concomitant use of pimozone, terfenadine, astemizole, or cisapride.
 
• Patient is enrolled in another clinical trial where antiemetic treatment is pre-specified by the study protocol.
 

---

STUDY DURATION	This study will last approximately 20 months from 1 st patient enrolled until last patient has completed. The observation period for each subject will last 4-6 months.
RECRUITMENT PERIOD	Approximately 12 months
ANALYSIS	Descriptive statistics will be generated for the primary, secondary and exploratory endpoints.

Table 1: Time and event schedule

Activity	Screening/ Visit 1	Visit 2 Cycle 1	Visit 3 Cycle 2	Visit 4 Cycle 3	Visit 5 Cycle 4	Visit 6/Final visit
Time period	-28 days to Day 1, Cycle 1	Day 1 of Cycle 1	Day 1 of Cycle 2	Day 1 of Cycle 3	Day 1 of Cycle 4	Within 28 days of Cycle 4 or prior to start of next chemotherapy cycle
Informed consent	X					
Inclusion/Exclusion	X					
Demographics & Medical History	X					
Nausea assessment - physician	X					
Current treatments/medications	X					
Patient Kit (distribute and provide education on use)	X*					
Patient Assessments:						
Patient diary, including: 
 
• Nausea Severity Assessment
 
• Rescue medications
 
• Adverse Events
 
		X 	X 	X 	X 	
• Functional Living Index – Emesis (FLIE)		X 	X 	X 	X 	
• Work Productivity Activity Impairment Scale – Nausea and Vomiting (WPAI-NV)		X 	X 	X 	X 	
Patient Kit - collect and review diary and questionnaires			X	X	X	X
Concomitant medication		X	X	X	X	X
Adverse event		X	X	X	X	X
Study completion assessment/early discontinuation						X

\*Patient Kit can be distributed at Screening/Visit 1 or Visit 2. All assessments/training should be completed prior to chemotherapy treatment

 Patient completes diary on days 1-5 (0-120 hours) post chemotherapy cycle

 Patient completes FLIE and WPAI after day 5 of cycle

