### 6.8.2 Patient Diary

The patient diary will be completed daily for the first five days of each cycle (starting on the day chemotherapy is administered). The patient diary will report daily occurrence and intensity of nausea (utilizing a VAS) and vomiting, rescue medications, adverse events (excluding nausea and vomiting), concomitant medication use for CINV.

The patient diary will be included in the Patient Kit will be distributed at Visit 1 and collected at Visits 3 through 6.

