**Appendix 8: Study Drug Access Card**

## Appendix 2: Patient Diary

Dear patient,

This booklet contains a diary which you should complete daily during your participation in this study. The patient daily diary will be used to capture the nausea and vomiting you experienced, the medication for the treatment of nausea and/or vomiting you took and to assess the effectiveness of the study treatment in controlling nausea and vomiting. The diary will be collected during study visits and reviewed with you by study personnel.

Please read the instructions carefully before filling the diary. If you have any questions regarding the diary, please contact study personnel.

There are no right or wrong answers. All information you provide will be strictly confidential.

Thank you for your participation in this study.

---

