### NAUSEA

To help assess how good or bad your nausea is, we have drawn a scale which ranges from 0 (no nausea) to 100 (nausea as bad as it could be). Each day, for the first 5 days following chemotherapy, we would like you to indicate on this scale how good or bad your nausea was, in your opinion. Please draw a straight vertical line on the scale to indicate how good or bad your nausea was each day. Please see an example below.

CAN-PRO-NEPA-001	PATIENT DIARY DAILY EVALUATION	   -    - 
		Site Number      Patient Number      Cycle #

DAY 1 EVALUATION: 0 - 24 HOURS AFTER START OF CHEMOTHERAPY				
Please complete the page on: <small>(for study personnel only)</small>	  /	   /	   	  :  
	<small>dd</small>	<small>mmm</small>	<small>yyyy</small>	<small>hh</small> : <small>mm</small>

Please remember to record any experience of retching (unproductive vomiting) and/or vomiting on pages 12 to 13 and the medication(s) you took for the treatment of nausea and/or vomiting on pages 14 to 15.

Please evaluate your severity of nausea for the 0 to 24-hour interval after the start of chemotherapy.

Example: Start of chemotherapy – 01June2018 @ 08:00  
 Period of evaluation = 01June2018 @ 08:00 to 02June2018 @ 07:59

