**4. Did you take any medications because of severe nausea?**

- No
- Yes → Please record on the Rescue Medication page (page 14).

CAN-PRO-NEPA-001	PATIENT DIARY	
 
  	 	 	-	 	 	 	-	 	
 
 Site Number		Patient Number		Cycle #	
 
				-				-		Site Number				Patient Number				Cycle #
					-				-											
Site Number				Patient Number				Cycle #												
	DAILY EVALUATION																			

DAY 2 EVALUATION: >24 - 48 HOURS AFTER START OF CHEMOTHERAPY																													
Please complete the page on: (for study personnel only)	
 
  	 	/	 	 	 	/	 	 	 	 	:	 	 	
 
 dd		mmm		yyyy		hh	mm	
 
			/				/					:			dd			mmm				yyyy					hh	mm
		/				/					:																		
dd			mmm				yyyy					hh	mm																

Please remember to record any experience of retching (unproductive vomiting) and/or vomiting on pages 12 to 13 and the medication(s) you took for the treatment of nausea and/or vomiting on pages 14 to 15.

Please evaluate your severity of nausea for the >24 to 48-hour interval after the start of chemotherapy.

Example: Start of chemotherapy – 01June2018 @ 08:00  
 Period of evaluation = 02June2018 @ 08:00 to 03June2018 @ 07:59

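### The protocol makes the Day 1–5 diary a record of adverse events, but the Appendix 2 diary has no place for them, so non-serious events are likely to be under-reported

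*Combined protocol and SAP*

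**What the plan says.** Three places in the protocol assign adverse events to the diary.

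- Section 3.1 has patients report "adverse events (excluding nausea and vomiting) in a diary from Day 1 (chemotherapy treatment day) to Day 5".
- Section 6.8.2 lists the diary's daily content as including "rescue medications, adverse events (excluding nausea and vomiting), concomitant medication use for CINV".
- Table 1 has a patient diary row, marked for cycles 1 to 4, with "Adverse Events" as one of its three components.

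Section 1.2 adds that the parameters of interest are collected by diary and then entered in the eCRF.

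Appendix 2 describes the diary to the patient differently: "The patient daily diary will be used to capture the nausea and vomiting you experienced, the medication for the treatment of nausea and/or vomiting", together with how well treatment controlled them. Each day page ends with the question "Did you take any medications because of severe nausea" and carries the reminder "Please remember to record any experience of retching (unproductive vomiting) and/or vomiting on pages 12 to 13", followed by a pointer to the antiemetic medication log. Adverse events are not mentioned.

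Section 3.7 evaluates safety by the incidence and type of adverse events. Section 8.3 has the investigator enter events that the patient reports during a visit.

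**The concern.** A patient following the protocol is meant to note any other symptom daily over the first 120 hours. On the printed diary, someone with constipation or headache on Day 2 (the common reactions named in section 1.4) finds no question or log for it. If the event does not lead to an emergency visit or overnight stay, and nobody reports it earlier, it is first raised at the next scheduled visit.

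The incidence of non-serious events is at stake. The study is meant to support the development programme's data, safety included (sections 1.2 and 7.1), and a daily record is a different collection method from a question asked at the next cycle. Detail is also at stake. The form in Appendix 6a asks for start and end dates, a duration class (under 1 hour, 1–24 hours, over 24 hours), and intensity at onset and at maximum. Such facts are harder to establish without a note made at the time.

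**Working it through.** There is no stated figure to reproduce. Sections 3.3 and 7.2 say no formal sample size calculation was done, and section 7.3 makes all analyses descriptive. The check is a comparison of texts, then an illustration of scale.

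**1. What Appendix 2 contains**

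| Part of the diary | Content | Adverse event entry? |
|---|---|---|
| Letter and instructions | Nausea, vomiting, medication for them, effectiveness | No |
| Five day pages, four items each | Nausea scale, vomiting, appetite (worded around nausea), medication for severe nausea | No, 0 of 4 items on each page |
| Retching/vomiting log | Episodes with times | No |
| Rescue medication log | Medication for nausea or vomiting | No |
| Emergency visit and overnight stay page | Reason, including another reason, with date and times | Only for events leading to such a visit or stay |
| Closing page | Thanks and return instruction | No |

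**2. Could a page be missing from the appendix?** The table of contents starts Appendix 2 on page 49 and Appendix 3 on page 59, so Appendix 2 has 59 − 49 = 10 pages. Counting the letter and instructions as about one page, the parts above make 1 + 5 + 1 + 1 + 1 + 1 = 10. The diary's own numbering also fits: letter/instructions 1, day pages 5, FLIE 3 and WPAI-NV 2 (assumed order) give 11, so the vomiting log starts on page 12, as the reminder says. One loose end remains. The diary cites pages 12–13 and 14–15 for its two logs, but the appendix prints one sheet of each. The issued booklet should be checked.

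**3. When the next question is asked.** Under section 3.1, Visit 2 precedes the first chemotherapy and Visits 3 to 5 fall on Day 1 of cycles 2 to 4. The documents give no cycle length. If cycles last 21 days (assumption), the next visit is on Day 22. The gap is 22 − 5 = 17 days for a Day 5 event and 22 − 1 = 21 days for a Day 1 event. With 28-day cycles (assumption) it is 29 − 5 = 24 to 29 − 1 = 28 days. After cycle 4, Table 1 places Visit 6 within 28 days or before the next cycle, so that gap can be shorter.

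**4. Scale, as illustration only.** Section 1.4 gives three rates for patients on netupitant 300 mg with palonosetron: 5.2% in cycle 1 of Study 3, 8.1% in Study 2 and 50% in Study 1. Patients counted = 200 × rate × captured share, where every captured share below 100% is an assumption.

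| Background rate | All captured | 90% | 70% | 50% |
|---|---|---|---|---|
| 5.2% | 10.4 | 9.4 | 7.3 | 5.2 |
| 8.1% | 16.2 | 14.6 | 11.3 | 8.1 |
| 50% | 100 | 90 | 70 | 50 |

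The rates are not interchangeable. The 5.2% covers one cycle in a study where 76% received moderately emetogenic chemotherapy, and the text does not plainly call it treatment-related. The 8.1% comes from an anthracycline-cyclophosphamide population and the 50% from a single cisplatin cycle. This study follows four cycles of highly emetogenic chemotherapy, and section 3.7 counts events regardless of cause.

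**The case against.** The strongest reply is that safety reporting does not depend on the diary. The lists of diary-derived parameters in sections 2.2 and 6.7 omit adverse events, and sections 6.9 and 8.3 describe reporting without it. Section 6.9 lets the subject, a caregiver or a representative report from consent through follow-up, and section 3.1 says patients will report safety events between cycles. Visits 3 to 6 include adverse event and concomitant medication assessments, so the question is a prompted one. Charts and hospital records are source documents under section 12.2. On this view the three diary mentions may be a drafting slip.

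Much of this stands. A reader might infer that recall at the next visit is the only source for Day 1–5 events. The documents do not support that, given the other reporting routes and the emergency visit and overnight stay page. The exposed group is narrower: non-serious events that lead to no such visit or stay and are not reported or charted beforehand. The reply also shows that correcting the protocol text is a legitimate alternative to changing the diary.

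It does not remove the mismatch. Three places promise a daily patient record that the printed diary cannot supply, and the reporting routes outside the diary provide no daily tool in its place.

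**Conclusion.** The point holds as an internal inconsistency with a likely effect on data quality. Table 1 and sections 3.1 and 6.8.2 cannot be carried out with the Appendix 2 diary. Non-serious Day 1–5 events therefore depend mainly on questioning at the next visit. Their incidence is likely to be under-reported, and their dates and durations to be less reliable.

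A reader might go further and conclude that events will be under-counted by a definite fraction. The documents do not support that: they give no capture rate, and the number of patients with an event runs from about 10 to 100 of 200 depending on which background rate is used. The direction is a judgement about recall over an interval of weeks; the size is unknown. Reporting of serious events does not rest on the diary.

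The conclusion assumes that the issued booklet matches Appendix 2. If it already has an adverse event page, only the appendix needs updating.

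**What to change.** Check the issued booklet first. If it has no such page, add one log page to Appendix 2 titled *Other symptoms or health problems (not nausea, retching or vomiting)*, with yes/no, description, start and stop date and time, and whether medication was taken. Put a reminder line on each day page, like those for the existing logs. Sites review the page at Visits 3 to 6 and transcribe entries to the adverse event form.

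For cycles completed on the present diary, report adverse event rates by diary version, or state that those events were collected by recall at visits. One patient may use both versions, so tabulate this by cycle.

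If the sponsor intends collection at visits only, correct Table 1 and sections 3.1 and 6.8.2 instead, and report the rates as recall-based.

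The diary change costs a revised booklet with research ethics board review (section 11.1 requires this for updated subject materials), slightly more patient writing and site transcription, and possibly a higher reported adverse event rate. Correcting the text alone is cheaper but leaves the data as they are.
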